5.2.5 REMOVAL OF SUBJECTS FROM THERAPY OR ASSESSMENT

A subject **may** be withdrawn from the trial if:

- 1. An SAE occurs.
- 2. The subject fails to comply with the protocol requirements or to cooperate with the investigator.
- 3. The subject starts disallowed treatment (see Section 5.3.12). The sponsor should be contacted to evaluate the need for withdrawal.
- 4. The subject demonstrates lack or loss of treatment response during the trial.

A subject **must** be withdrawn from the trial if:

- 1. The parent(s) or legal representative(s) withdraw(s) consent, or the subject withdraws consent or assent.
- 2. The investigator considers it, for safety reasons, in the best interest of the subject that he or she be withdrawn.
- 3. Pregnancy has been determined.
- 4. The subject is diagnosed with acute hepatitis A, B, or C infection after baseline. For details on monitoring and management of hepatitis, see Section 5.5.4.

- 5. The subject experiences a grade 3 or 4 cutaneous reaction/rash (according to the DAIDS scale; see Section 7.2, Addendum 2: DAIDS Grading Table). For details on monitoring and management of cutaneous reaction/rash, see Section 5.5.1.
- 6. The subject experiences a grade 4 AE considered at least possibly related to DRV/rtv or a confirmed grade 4 laboratory abnormality (according to the Division of AIDS [DAIDS] scale; see Section 7.2, Addendum 2: DAIDS Grading Table) considered at least possibly related to DRV/rtv. Exceptions are, unless clinical assessment foresees an immediate health risk to the subject:
- 7. Subjects with asymptomatic triglyceride grade 4 elevations (see Section 5.6.2). The subject experiences a persistent grade 3 or 4 glucose elevation despite appropriate anti-hyperglycemic treatment (except if the subject has pre-existing diabetes; see Section 5.6.1)
- 8. The subject experiences a confirmed grade 4 pancreatic amylase elevation or a confirmed grade 3 or grade 4 lipase elevation, which persists after 14 days after the interruption of the trial medication, or if the toxicity recurs more than twice (see also Section 5.6.5.2). The subject experiences, after trial medication interruption because of a confirmed grade 3 increase in alanine aminotransferase (ALT) or aspartate aminotransferase (AST), a confirmed recurrence of grade 3 or 4 increase in ALT or AST. For subjects with hepatitis B or C coinfection present at baseline, refer to Section 5.5.3 for toxicity management plans.

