5.5 Safety Monitoring and Toxicity Management

Toxicity management is at the discretion of the investigator, and is to take into account the protocol-defined procedures defined under 5.5.1, 5.5.2, 5.5.3, 5.5.4, 5.5.5, 5.5.6, 5.5.7, and 5.5.8, and the local standard clinical practice.

After termination of data collection, toxicity management will be performed per local standard of care and documented in the subject's medical records only.

The following guidelines are present in the Clinical Trial Protocols for ongoing HIV-1 trials of DRV. Participating investigators are strongly encouraged to follow these guidelines and to apply the same safety measures for subjects participating in this trial.

Note:For grade 3 or 4 laboratory toxicities, a confirmatory measurement within 48 hours after the laboratory results become available is mandatory. This management scheme is for confirmed laboratory abnormalities and not for isolated events.

The following laboratory abnormalities do not warrant mandatory confirmation within 48 hours:

- Subjects with asymptomatic triglyceride or cholesterol elevations of grade 3 or 4.

All adverse events occurring at any time during the trial will be followed until satisfactory clinical resolution (i.e., value back to baseline value) or stabilization or until final database lock. All grade 3 and grade 4 laboratory abnormalities and laboratory abnormalities resulting in an increase of 2 DAIDS grades from baseline will be followed until return to baseline or within 1 grade from baseline. Certain long-term adverse events of ARV therapy cannot be followed to resolution within the setting of this protocol; in these cases follow-up will be the responsibility of the treating physician, which will be agreed upon with the sponsor.

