5.5.1 CUTANEOUS REACTION/RASH

DRV is a sulfonamide. Subjects who previously experienced a sulfonamide allergy will be allowed to enter the trial. To date, no potential for cross sensitivity between drugs in the sulfonamide class and DRV has been identified in subjects participating in Phase II/III adult trials as well as Phase II pediatric trials with HIV-1 infected subjects aged > 6 years.

Management will be at the discretion of the investigator, taking into account the following protocol-defined procedures, and should follow generally accepted medical standards. Cetirizine, levocetirizine, topical corticosteroids, and antipruritic agents will be allowed at the investigator's discretion for all grades of rashes.

Grade 1 and 2 Cutaneous Reaction/Rash

A grade 1 cutaneous reaction/rash is defined as localized macular rash.

A grade 2 cutaneous reaction/rash is defined as diffuse macular, maculopapular or morbilliform rash, or target lesions.

Subjects experiencing a grade 1 or grade 2 rash or cutaneous reaction may continue treatment or have their trial medication interrupted at the investigator's discretion. Local safety sampling at the time of the rash and clinical follow-up for these adverse events will be at the discretion of the investigator, however, close clinical follow-up is recommended to monitor for any progression of the adverse event.

The subject should be advised to contact the investigator immediately if there is any worsening of the rash, if any systemic signs or symptoms worsen, or if mucosal involvement develops.

Grade 3 and 4 Cutaneous Reaction/Rash

A grade 3 cutaneous reaction/rash is defined as:

- Diffuse macular, maculopapular or morbilliform rash with vesicles or limited number of bullae
- Superficial ulcerations of mucous membrane limited to 1 site*
- Cutaneous reaction/rash with at least 1 of the following*:
 - 1. Elevations of ALT and/or AST $> 2 \times$ baseline but at least $5 \times$ ULN;
 - 2. Fever $\geq 38^{\circ}$ C or 100° F;
 - 3. Serum sickness-like reaction;
 - 4. Eosinophil count > 1000/mm³.
 - * Revised by the sponsor.

A grade 4 cutaneous reaction/rash is defined as:

- Extensive or generalized bullous lesions;
- Stevens-Johnson syndrome (SJS);
- Ulceration of mucous membrane involving 2 or more distinct mucosal sites;
- Toxic epidermal necrolysis (TEN).

A visit schedule for cutaneous reaction/rash follow-up is provided in Table 5 below.

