Subjects experiencing a grade 3 or 4 rash or cutaneous event must have their study medication discontinued and be withdrawn from the trial (see Section 5.2.5 and see Section 7.3, Addendum 3: Visit Schedule for Cutaneous Reaction/Rash Follow-up for pediatric subjects). Referral to a dermatologist and biopsy are required for these events. To minimize distress of skin biopsies, the skin should be anesthetized by application of an anesthetic cream and/or an intradermal injection of 1-2% lidocaine. At the discretion of the investigator and after approval of the sponsor, local safety testing of the following parameters is required to determine possible liver or systemic abnormalities: ALT, AST, bilirubin (total, direct and indirect), creatinine and a complete blood cell count (including hemoglobin, hematocrit, red blood cell (RBC) and white blood cell (WBC) count, neutrophils, lymphocytes, monocytes, eosinophils, basophils and platelet count). Close clinical follow-up and appropriate medical intervention should be instituted for these events; daily follow-up is recommended for 5 days from the onset of the event to monitor for progression of the event and weekly afterwards.

Subjects should be advised to contact the investigator immediately if they notice any worsening of the rash.

Table 5: Visit Schedule for Cutaneous Reaction/Rash Follow-up

DAIDS Toxicity Grade	Definitions	Investigator Action
Grade 1	Localized macular rash	May continue trial medication or have their trial medication interrupted at the investigator's discretion.
Grade 2	Diffuse macular, maculopapular or morbilliform rash Target lesions	May continue trial medication or have their trial medication interrupted at the investigator's discretion.
Grade 3	Diffuse macular, maculopapular or morbilliform rash with vesicles or limited number of bullae Superficial ulcerations of mucous membrane limited to 1 site* Cutaneous reaction/rash with at least 1 of the following*: - Elevations in ALT and/or AST (> 2 × baseline but at least 5 × ULN) - Fever ≥ 38°C or 100°F - Serum sickness-like reaction - Eosinophils > 1000/mm³ * Revised by the sponsor	Permanently discontinue trial medication (see Section 5.2.5). Referral to a dermatologist and biopsy are required for these events (preferably within 24 hours). Local laboratory assessments can be performed at the discretion of the investigator and after approval of the sponsor. Daily follow-up visits for the first 5 days and weekly afterwards.

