PARAMETER	GRADE 1 MILD	GRADE 2 MODERATE	GRADE 3 SEVERE	GRADE 4 POTENTIALLY LIFE- THREATENING
Pruritis associated with injection See also Skin: Pruritis (itching - no skin lesions)	Itching localized to injection site AND Relieved spontaneously or with < 48 hours treatment	Itching beyond the injection site but not generalized OR Itching localized to injection site requiring ≥ 48 hours treatment	Generalized itching causing inability to perform usual social & functional activities	NA
SKIN – DERMATOLOGI		I mi · · · · · · · · · · · · · · · · · ·		Lara
Alopecia	Thinning detectable by study participant (or by caregiver for young children and disabled adults)	Thinning or patchy hair loss detectable by health care provider	Complete hair loss	NA
Cutaneous reaction/rash	Localized macular rash	Diffuse macular, maculopapular, or morbilliform rash OR Target lesions	Diffuse macular, maculopapular, or morbilliform rash with vesicles or limited number of bullae OR Cutaneous reaction/rash with superficial ulcerations of mucous membrane limited to 1 site ^a OR Cutaneous reaction/rash with at least 1 of the following ^a : elevation of AST and/or ALT > 2 x baseline but at least > 5 x ULN ^a ; fever (> 38°C or 100°F) a, eosinophils > 1000/mm ^{3a} ; serum sickness-like reaction ^a	Extensive or generalized bullous lesions OR Stevens-Johnson syndrome (SJS) OR Ulceration of mucous membrane involving 2 or more distinct mucosal sites OR Toxic epidermal necrolysis (TEN)
Hyperpigmentation	Slight or localized	Marked or generalized	NA	NA
Hypopigmentation	Slight or localized	Marked or generalized	NA	NA
Pruritis (itching – no skin lesions) (See also Injection site reactions: Pruritis associated with injection)	Itching causing no or minimal interference with usual social & functional activities	Itching causing greater than minimal interference with usual social & functional activities	Itching causing inability to perform usual social & functional activities	NA
CARDIOVASCULAR	1 4 4 4 4 4 4 4 4 4 4 4 4 4 4 4 4 4 4 4		10	T:0 4
Cardiac arrhythmia (general) (By ECG or physical exam)	Asymptomatic AND No intervention indicated	Asymptomatic AND Non- urgent medical intervention indicated	Symptomatic, non-life threatening AND Non- urgent medical intervention indicated	Life-threatening arrhythmia OR Urgent intervention indicated

a Revised by the sponsor.

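### The fever item that alone makes a rash grade 3, and so forces withdrawal, pairs 38°C with 100°F, which are different temperatures; its inequality sign also differs between 5.5.1 and Addendum 2

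*Protocol*

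**What the plan says.** The grade 3 definition in Protocol 5.5.1 includes a "Cutaneous reaction/rash with at least 1 of the following" of four findings. The second is "Fever ≥ 38°C or 100°F", and Table 5 repeats it. The sponsor marks the list as its own revision. The rash row of Addendum 2 (Protocol 7.2) has the same sponsor-revised item as "fever (> 38°C or 100°F".

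The grade decides what happens to the subject:

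- Grades 1 and 2 (5.5.1): "Subjects experiencing a grade 1 or grade 2 rash or cutaneous reaction may continue treatment", or have it interrupted, as the investigator judges.
- Grades 3 and 4 (5.5.1): subjects "must have their study medication discontinued and be withdrawn from the trial". Table 5 gives the action as "Permanently discontinue trial medication (see Section 5.2.5", and requires referral to a dermatologist and a biopsy.
- Must-withdraw criterion 5 in 5.2.5: "The subject experiences a grade 3 or 4 cutaneous reaction/rash (according to the DAIDS scale; see Section 7.2, Addendum 2: DAIDS Grading Table". This criterion takes the grade from Addendum 2 and refers to 5.5.1 for management.

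For pediatric subjects, Addendum 3 (7.3) has its own rash schedule. It lists dermatologist referral and biopsy at grades 1 and 2 as well as at grades 3 and 4.

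**The concern.** One of the four findings is enough, so temperature alone can move a rash from a grade at which treatment may continue to one at which the subject must leave the trial. Such a limit should give one answer for one temperature. Here the Celsius and Fahrenheit values are offered as if they were the same point, and they are not. A site that reads in Fahrenheit, or that takes *or* to mean that either limit suffices, applies a lower threshold than a site that works in Celsius. The ≥ and > signs add a second, smaller discrepancy between the management table and the grading table that 5.2.5 relies on.

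An error in either direction has a cost. Inclusion criterion 3 admits only subjects who cannot get darunavir commercially, reimbursed or from another source, and supplying it is the primary objective. Withdrawing a subject on a misprinted limit ends that supply. Missing a true grade 3 event leaves a subject with a febrile rash on the drug.

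**Working it through.** Inputs: the fever item in 5.5.1 and Table 5 (≥, 38°C, 100°F) and in Addendum 2 (>, 38°C, 100°F). No sample size, power or alpha is involved.

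**Is the printed pair equivalent?**

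- °F = °C × 9/5 + 32, so 38 × 9/5 + 32 = 100.4°F.
- °C = (°F − 32) × 5/9, so (100 − 32) × 5/9 = 37.78°C.
- The gap is 100.4 − 100 = 0.4°F, or 38 − 37.78 = 0.22°C.

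The pair agrees only if 37.78 is rounded to a whole degree. The general fever row of Addendum 2 grades to one decimal, with grade 1 starting at 37.7°C, so whole-degree rounding is not the precision used for fever elsewhere.

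**Which readings change grade?** The table assumes that each inequality sign also applies to the Fahrenheit value, and that the rash has no other grade 3 feature. *Either limit* is the literal reading of *or*. An entry of yes means grade 3.

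| Reading | ≥ 38°C (5.5.1, Table 5) | > 38°C (Addendum 2) | ≥ 100°F (5.5.1, Table 5) | > 100°F (Addendum 2) | Either limit, 5.5.1 and Table 5 | Either limit, Addendum 2 |
|---|---|---|---|---|---|---|
| 37.7°C (99.86°F) | no | no | no | no | no | no |
| 37.8°C (100.04°F) | no | no | yes | yes | yes | yes |
| 37.9°C (100.22°F) | no | no | yes | yes | yes | yes |
| 38.0°C (100.40°F) | yes | **no** | yes | yes | yes | yes |
| 38.1°C (100.58°F) | yes | yes | yes | yes | yes | yes |
| 99.9°F (37.72°C) | no | no | no | no | no | no |
| 100.0°F (37.78°C) | no | no | yes | **no** | yes | **no** |
| 100.1 to 100.3°F (37.83 to 37.94°C) | no | no | yes | yes | yes | yes |
| 100.4°F (38.00°C) | yes | **no** | yes | yes | yes | yes |
| 100.5°F (38.06°C) | yes | yes | yes | yes | yes | yes |

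**Reading the table.**

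- *Unit mismatch.* At 37.8 and 37.9°C, and at 100.1 to 100.3°F, the Celsius limit gives no and the Fahrenheit or either-limit reading gives yes, in all three places. At 100.0°F the same split occurs in 5.5.1 and Table 5.
- *Sign mismatch* (bold). It matters at exactly 38.0°C (100.4°F), and then only if the Celsius limit is applied alone. It also matters at exactly 100.0°F, if the Fahrenheit limit or the literal *or* is applied.
- From 38.1°C (100.5°F) upward, and at 37.7°C (99.9°F) and below, every reading agrees.

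**The case against.** The best case against the point has four parts.

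1. *A tie-break exists.* The general instructions in Addendum 2 tell the grader to choose the higher grade when an event could fall in either of two, and 5.2.5 grades rash by Addendum 2. This would favour grade 3 if a site noticed the conflict. A site that looks only at the limit in its own unit sees no conflict, so the rule is not triggered. If it were always applied, 100°F would become the working limit and the printed 38°C would do nothing. It does not correct the text.

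2. *Discretion and simplified follow-up.* Section 5.5 leaves toxicity management to the investigator, and it adds: "After termination of data collection, toxicity management will be performed per local standard of care". This narrows the period in which 5.5.1 is the operative guide. The must-withdraw list in 5.2.5 is separate and remains in the current text, and criterion 5 leaves no discretion. The investigator may withdraw a subject for safety at any temperature, but has no matching freedom to keep one with a grade 3 rash.

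3. *The sign conflict can be overstated.* A reader might infer that Addendum 2 denies grade 3 at exactly 38.0°C. On the literal *or* it does not, because 38.0°C is 100.4°F and exceeds 100°F. This part of the objection stands, so the sign is a secondary fault. If every site applied *or* literally, the three places would agree at every one-decimal Celsius reading, and the only split between them would be at 100.0°F.

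4. *The consequences can be overstated.* A reader might infer that the threshold decides referral and biopsy for everyone. For pediatric subjects it does not, since Addendum 3 already prescribes both at grades 1 and 2. For them it decides only discontinuation, withdrawal and the later visit schedule. This part also stands.

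It is also true that no document shows a site using Fahrenheit, and that the general fever row of Addendum 2 is in Celsius only.

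**Conclusion.** The point holds. The main fault is the unit pairing, which is certain from the text: a limit that alone triggers mandatory withdrawal is printed as two temperatures 0.22°C apart, in all three places. The sign difference is real but affects only single readings, under the conditions shown in the table.

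For an affected subject, the grade decides mandatory discontinuation and withdrawal. In adults it also decides the required dermatology referral and biopsy.

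The scale is small. Disagreement is confined to 37.8 to 38.0°C, or 100.0 to 100.4°F, in a rash with no other grade 3 feature. The documents give no rash count and do not say which sites use Fahrenheit, so the number of subjects is unknown and likely small. Nothing here shows that anyone was wrongly withdrawn or wrongly kept on treatment.

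A reader might infer that the safety conclusions are compromised. The documents do not support that. The trial tests no hypothesis (SAP 1.3) and has no sample size calculation (Protocol 5.7.1). Only descriptive output is touched: AEs of grade 3 or higher and AEs leading to discontinuation (SAP 4.1.1), and reasons for discontinuation (SAP 3.2).

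The assumptions are that each sign carries over to the Fahrenheit value and that temperatures are recorded to one decimal. The correction should be made, because the error is certain, the consequence for an affected subject is serious, and the repair is cheap.

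**What to change.** Ask the sponsor which limit was intended. Then print one limit with one sign in the 5.5.1 text, Table 5 and the rash row of Addendum 2: ≥ 38.0°C (100.4°F), or ≥ 37.8°C (100°F) if the sponsor confirms the lower limit. Put the Fahrenheit value in parentheses as a conversion, so that it cannot be read as a second limit.

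The cost is one confirmation and three wording edits to the protocol. Data collection and the SAP do not change.

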5.5.2 ACUTE SYSTEMIC ALLERGIC REACTION

A summary of allergic reactions is provided in Table 6 below.

Subjects should be followed until resolution of the AE.

Grade 1 (localized urticaria [wheals] with no medical intervention indicated):

Subjects may continue medication for a grade 1 acute systemic allergic reaction. The subject should be advised to contact the investigator immediately if there is any worsening of the allergic reaction, or if any systemic signs or symptoms develop. Antihistamines or topical corticosteroids or antipruritic agents may be prescribed as long as these are in line with the package inserts of the ARVs (including DRV/rtv and background regimen) and with (dis)allowed medication for DRV indicated in Section 5.3.5.

Grade 2 (localized urticaria with medical intervention indicated or mild angioedema with no medical intervention indicated):

Subjects may continue medication for a grade 2 acute systemic allergic reaction. The subject should be advised to contact the investigator immediately if there is any worsening of the allergic

reaction; the subject should discontinue the trial medication and be withdrawn from the trial. Antihistamines or topical corticosteroids or antipruritic agents may be prescribed as supportive care as long as these are in line with the package inserts of the ARVs (including DRV/rtv and background regimen) and with (dis)allowed medication for DRV indicated in Section 5.3.5.

Grade 3 (generalized urticaria, angioedema with medical intervention indicated, or symptomatic mild bronchospasm):

Subjects will permanently discontinue medication (including DRV/rtv and background regimen) and will be withdrawn from the trial. Subjects will be treated as clinically appropriate. Standard management should be undertaken.

Grade 4 (acute anaphylaxis, life-threatening bronchospasm, or laryngeal edema):

Subjects will permanently discontinue medication (including DRV/rtv and background regimen) and will be withdrawn from the trial. Subjects will be treated as clinically appropriate. Standard management should be undertaken.

Table 6: Summary of Allergic Reaction

DAIDS Toxicity Grade	Definitions	Investigator Action
Grade 1	Localized urticaria (wheals) with no medical intervention indicated	May continue trial medication or have their trial medication interrupted at the investigator's discretion
Grade 2	Localized urticaria with medical intervention indicated, or mild angioedema with no medical intervention indicated	May continue trial medication or have their trial medication interrupted at the investigator's discretion
Grade 3	Generalized urticaria, or angioedema with medical intervention indicated, or symptomatic mild bronchospasm	Permanently discontinue trial medication
Grade 4	Acute anaphylaxis, or life-threatening bronchospasm, or laryngeal edema	Permanently discontinue trial medication

5.5.3 AST AND ALT ELEVATIONS

A summary of AST and ALT elevations is provided in Table 7 below.

Note: For grade 3 or 4 laboratory toxicities, subjects should have a confirmatory measurement within 48 hours after the laboratory results become available. This management scheme is for confirmed laboratory abnormalities and not for isolated events.

Grade 3 AST or ALT elevations ($> 5.0 - \le 10.0 \times ULN$):

Subjects are to interrupt all medication (including DRV/rtv and background regimen) except if they are coinfected with hepatitis B or C (see below). Upon resolution of the laboratory abnormality to within 1 grade level (\leq grade 2), the subject may resume all trial medication under the guidance of the investigator and after discussion with a sponsor physician.

If after a grade 3 elevation, the subject has a recurrence of a grade 3 or 4 increase in AST or ALT after restarting trial medications, he/she will permanently discontinue the medication (including DRV/rtv and background regimen) and will be withdrawn from the trial.

Subjects with concomitant hepatitis B and with emtricitabine (FTC) or lamivudine (3TC) as a component of the background regimen:

Warning: Severe acute exacerbations of hepatitis B have been reported in subjects who are co-infected with hepatitis B virus and HIV and have discontinued FTC or 3TC. Hepatic function should be monitored closely with both clinical and laboratory follow-up for at least several months in subjects who discontinue FTC or 3TC and are co-infected with hepatitis B virus and HIV. If appropriate, initiation of anti-hepatitis B therapy may be warranted.

Subjects with concomitant hepatitis A, B, C, or E:

Subjects with concomitant acute hepatitis A infection diagnosed at or after baseline have to be excluded. If acute viral hepatitis is diagnosed while on trial, the subject must be withdrawn immediately and the necessary follow-up visits performed.

Subjects with chronic hepatitis B or C coinfection are allowed to participate. These subjects will be allowed to continue treatment (including DRV/rtv and background regimen) if they develop a grade 3 elevation in AST or ALT provided alkaline phosphatase (ALP) is not elevated to grade 2 or higher and total bilirubin is not elevated to grade 3 or higher or subjects do not have signs and symptoms of clinically active hepatitis. Signs and symptoms of active hepatitis include, but are not limited to fatigue, malaise, anorexia, nausea, dark urine and clay-colored stools, bilirubinuria, jaundice, and liver tenderness. If signs or symptoms of clinically active hepatitis occur, or if AST or ALT increases to grade 4 elevations, then all treatment (including DRV/rtv and background regimen) will be permanently discontinued and the subject will be withdrawn from the trial.

In regions where hepatitis E is endemic, it is recommended that hepatitis E serologies be tested for the evaluation of unexplained increases of AST or ALT. Subjects diagnosed with acute hepatitis E at or after screening must be withdrawn immediately.

However, if subjects with chronic hepatitis B or C co-infection and with grade 3 elevation in AST or ALT elect to interrupt treatment (including DRV/rtv and background regimen) and have a recurrence of grade 3 increase in AST or ALT they may continue provided ALP is not elevated to grade 2 or higher and total bilirubin is not elevated to grade 3 or greater or subjects do not have signs and symptoms of clinically active hepatitis. If signs or symptoms of clinically active hepatitis occur or if AST or ALT increases to grade 4 elevations, then all treatment (including DRV/rtv and background regimen) will be permanently discontinued and the subject will be withdrawn from the trial.

Grade 4 AST or ALT elevations ($> 10.0 \times ULN$):

Subjects will permanently discontinue treatment (including DRV/rtv and background regimen) and will be withdrawn from the trial.

Table 7: Summary of AST and ALT Elevations

Revised DAIDS Table for Grading Severity	Ranges	Investigator Action	Rechallenge Instructions
Grade 1	$\geq 1.25 - \leq 2.5 \times ULN$	May continue therapy	Not applicable
Grade 2	$> 2.5 - \le 5.0 \times ULN$	May continue therapy	Not applicable
Grade 3	> 5.0 - ≤ 10.0 × ULN	Interrupt HIV therapy until toxicity ≤ grade 2; if coinfected with hepatitis B or C: may continue if ALP is grade 2 or below, bilirubin grade 3 or below, and asymptomatic	Allowed once
Grade 4	> 10.0 × ULN	Discontinue therapy	No

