5.5.8 OTHER TOXICITIES

Grade 1

Subjects who develop a grade 1 AE or toxicity may continue intake of the trial medication.

Grade 2

Subjects who develop a grade 2 AE or toxicity may continue intake of the trial medication based on the investigator's clinical judgment.

Note: For grade 3 or 4 laboratory toxicities, subjects should have a confirmatory measurement within 48 hours after the laboratory results become available. This management scheme is for confirmed laboratory abnormalities and not for isolated events.

Grade 3

Subjects who develop a grade 3 AE or toxicity should interrupt all medications (including DRV/rtv and OBR) and may resume all therapy when the AE or laboratory abnormality resolved to within one grade level (\leq grade 2) of the subject's baseline. The following exceptions apply:

- subjects who experience an asymptomatic glucose elevation of grade 3 (See Section 5.6.1);
- subjects who experience asymptomatic triglyceride or cholesterol elevations of grade 3 (See Section 5.6.2);
- subjects who experience asymptomatic pancreatic amylase elevations of grade 3 with no past or active history of pancreatitis (provided lipase is within normal limits) (See Section 5.6.5);
- subjects who experience an AE that is considered not related or doubtfully related to the study medication.

Grade 4

Subjects experiencing a grade 4 AE or toxicity will permanently discontinue medication (including DRV/rtv and OBR).

The following exceptions apply:

- subjects who experience asymptomatic triglycerides elevations of grade 4 (see also Section 5.2.5);
- subjects who experience an AE that is considered not related or doubtfully related to the trial medication.

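### For subjects with chronic hepatitis B or C and grade 3 AST/ALT, the text of Protocol 5.5.3 and its Table 7 set different conditions for continuing treatment

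*Protocol*

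**What the plan says.** Protocol 5.5.3 first tells subjects with grade 3 AST or ALT to interrupt all medication, and exempts those co-infected with hepatitis B or C. It then gives the exempted group its own rule in three places.

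- **First text paragraph.** They may stay on treatment "provided alkaline phosphatase (ALP) is not elevated to grade 2 or higher and total bilirubin is not elevated to grade 3 or higher", followed by "or subjects do not have signs and symptoms of clinically active hepatitis".
- **Recurrence paragraph** (grade 3 returns after an elective interruption). The limits and the connective are the same: "they may continue provided ALP is not elevated to grade 2 or higher and total bilirubin is not elevated to grade 3 or greater", again followed by the 'or' clause on symptoms.
- **Table 7, grade 3 row.** Interrupt, but if co-infected "may continue if ALP is grade 2 or below, bilirubin grade 3 or below, and asymptomatic".

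Both text paragraphs add a stop rule. The first reads "If signs or symptoms of clinically active hepatitis occur, or if AST or ALT increases to grade 4 elevations", and the consequence is permanent discontinuation and withdrawal.

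The section presents the table as a restatement, not as a separate rule: "A summary of AST and ALT elevations is provided in Table 7 below".

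**The concern.** A summary table should give the same answer as the text that it summarises. This one differs in two respects at once. It admits ALP grade 2 and bilirubin grade 3, which the text's limits shut out, and it requires absence of symptoms as an additional condition where the text offers it as an alternative. The two differences pull in opposite directions, so whether the text or the table is stricter depends on how the text's 'or' is read.

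At stake is whether continuing DRV/rtv and the background regimen is permitted for certain co-infected subjects with raised liver tests. Either mistake has a cost. One keeps a subject on treatment beyond the limit that was meant. The other stops all antiretrovirals in a group for whom the same section warns about withdrawal of FTC or 3TC: "Severe acute exacerbations of hepatitis B have been reported in subjects who are co-infected with hepatitis B virus and HIV".

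**Working it through.** There is no planned figure to reproduce: the trial has no hypothesis and no sample size calculation. The check is an enumeration.

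**Inputs.** Let A be the ALP grade and B the total bilirubin grade, each 0 to 4 on the grading table in Addendum 2 (0 means below grade 1). AST or ALT is grade 3. The subject has no symptoms, because the stop rule in the text and the word 'asymptomatic' in the table both exclude symptomatic subjects. That leaves 5 × 5 = 25 combinations.

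**Table 7.** A ≤ 2 and B ≤ 3, so 3 × 4 = 12 combinations permit continuation.

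**Text.** The sentence has the form 'A < 2 and B < 3 or no symptoms', which can be grouped in three ways.

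| Grouping of the text | Permitted (symptom-free) | Text only | Table only |
|---|---|---|---|
| All three required ('or' meant as 'and'): A < 2, B < 3, no symptoms | 2 × 3 = 6 | 0 | 6 |
| Literal: (A < 2 and B < 3) or no symptoms | 25 | 13 | 0 |
| Mixed: A < 2 and (B < 3 or no symptoms) | 2 × 5 = 10 | 2 | 4 |

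The first grouping makes the text stricter than the table and the second makes it looser. Under the third, neither set contains the other: the text alone permits A = 0 or 1 with B = 4, and the table alone permits A = 2 with B = 0 to 3. None of the three equals the table.

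**Do other sections remove the difference?**

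- Section 5.2.5 refers co-infected subjects back to 5.5.3 for AST/ALT elevations, so it does not choose between the versions. Its item 6 (withdrawal for grade 4 abnormalities at least possibly related to DRV/rtv) removes A = 4 and B = 4. The text then permits 6, 16 or 8 against the table's 12, and still does not match.
- Section 5.5.8 tells subjects with other grade 3 toxicities to interrupt, unless the event is judged unrelated or doubtfully related. Applied to related ALP and bilirubin elevations, it limits both versions to A ≤ 2 and B ≤ 2. The table then permits 3 × 3 = 9. The text permits 6 (all three required), 9 (literal) or 6 (mixed). The two versions coincide only under the literal grouping, and only for elevations judged at least possibly related.

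**Two symptom-free examples.**

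- ALT 8 × ULN (grade 3), ALP 4 × ULN (grade 2), bilirubin 1.0 × ULN (grade 0). Table 7 permits continuation, as does the literal text. The other two groupings do not.
- ALT 8 × ULN, ALP 6 × ULN (grade 3), bilirubin 1.0 × ULN, judged unrelated. Table 7 does not permit continuation. The literal text does, and the other two groupings do not.

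**The case against.** The best reply is that little turns on this in practice, and most of that reply stands.

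- **Discretion.** Section 5.5 leaves toxicity management to the investigator and only encourages use of these guidelines. Both versions are permissive, and the text expressly provides for co-infected subjects who choose to interrupt. A site that interrupts breaches neither version. A reader might infer that the discrepancy makes compliant sites treat the same subject in opposite ways. The documents already allow that, so the real conflict is narrower: whether continuing is permitted in the boundary combinations.
- **No order to interrupt in the text.** A reader might infer that the text commands interruption once a laboratory limit is passed. It does not. It exempts co-infected subjects from the general grade 3 order and requires stopping only for symptoms or grade 4 AST/ALT. Interruption above the ALP or bilirubin limit is implied, not stated.
- **The counts may overstate the overlap.** Jaundice, dark urine and bilirubinuria are on the section's list of signs of active hepatitis, so many states with high bilirubin may already meet the stop rule. If B is restricted to 0 to 2, the table permits 9. The text permits 6, 15 or 6, a difference of 3, 6 or 3 combinations. The difference shrinks but does not disappear.
- **Short remaining life.** Under Amendment 2 the next planned visit ends data collection, and toxicity management then follows local standard of care. With visits at most 6 months apart, the rule has about one visit interval to run.

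None of this makes the section consistent. It limits the consequence.

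**Conclusion.** The inconsistency is established from the wording alone. The two laboratory limits differ by one grade each and the connective differs. On its own terms no reading of the text gives the Table 7 rule: 6, 25 or 10 combinations against 12.

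Two stronger conclusions are tempting. The first is that Table 7 is simply the laxer version. That holds only if 'or' was meant as 'and'; under the literal grouping the table is stricter, and under the mixed grouping neither is. The second is that the text's limits must be the intended ones. There is some support for reading 'or' as 'and', since the literal grouping combined with the stop rule leaves the twice-stated laboratory limits with no effect. But nothing in the documents says which limits the sponsor meant.

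Severity is minor. The counts are grade combinations and carry no frequencies, and the number of co-infected subjects is not given. SAP 1.2 states that local safety laboratory results were not transferred for formal analysis, so no planned analysis rests on these limits.

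**What to change.** State one rule in both text paragraphs and in the Table 7 grade 3 cell. Proposed wording: 'may continue only if ALP is grade 1 or below, total bilirubin is grade 2 or below, and there is no sign or symptom of active hepatitis; otherwise interrupt'. This replaces 'or' with 'and' in the two paragraphs, lowers each limit in the table cell by one grade, and makes explicit the interruption that the text now only implies.

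The sponsor's medical lead should confirm the limits before anything goes to sites. If the Table 7 limits are the intended ones, change both text paragraphs to the table's limits and to 'and', and leave the table's limits as they are.

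The drafting cost is one table cell, two connectives and the added consequence. Part II 6.2 requires IEC/IRB approval before a substantial amendment is implemented, so the approval route depends on how the change is classified. The clinical cost of the stricter wording is some more interruptions among co-infected subjects, with the hepatitis B flare risk on stopping FTC or 3TC that 5.5.3 describes.
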